We designed our analyses based on two study samples. Our main study sample comprised all employees who worked for any duration of time at BJ’s Wholesale Club during the study period. In other words, we included any worker who worked at BJ’s for any length of time during the study period. This is the most inclusive sample.

A potential drawback of these sample inclusion criteria is the possibility of endogenous entry or exit based on the treatment itself. For example, a worker’s decision to join or leave employment at BJ’s Wholesale Club could be a function of the availability of, or exposure to, the wellness program. Therefore, we also defined a relatively stable subsample of employees who were continuously employed at BJ’s in the months before the treatment. This “stably employed” subsample comprised all employees working at BJ’s during, at minimum, the 13 consecutive weeks immediately prior to the onset of the treatment—and thus cannot have entered because of the treatment. Exit from this sample might still be endogenous in theory, however. We will therefore gauge the potential bias introduced by any observed differences in exit between treatment and control sites using a bounding exercise. Additional details on the construction of this subsample are provided below and in the appendix.

B. Balance between treatment and control

We tested balance between treatment and control groups on observable baseline characteristics. We examined balance on demographic variables (age, sex, and race) for all of the analytical samples. We also examined balance on job and employment characteristics in the pre-intervention period for the stably employed subsample, as they by construction were in jobs with characteristics defined prior to the intervention and thus exogenous to the treatment status.

As **Table 8** demonstrates at the employee level, our randomly assigned worksites were balanced on many employee characteristics, but not all. Notably, while treatment and control site workers

⁸ This indicator was our primary definition of participation in our prior phase 1 analysis. Given that we expanded the sample size for phase 2 (with a different total number of modules available), we believe the continuous measure is preferable here.

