were similar on age and gender, a greater proportion of treatment site workers were white (and a lower proportion black and Hispanic) than individuals in control worksites. To address imbalance on some observable characteristics, we followed two common strategies. First, we weighted the treatment and control groups to be more balanced on observed characteristics (such that each group mirrors the overall employee population). Second, we include observable characteristics as covariates in the regression analyses below. Neither of these strategies, however, guarantees that there are no idiosyncratic differences in unobserved confounders.

The sample weights that we generate to address the imbalance on some demographics were constructed to balance treatment and control samples on age, sex, and race while minimizing variance of the weights for a given level of balance. A given level of balance is defined as the tolerance of a certain magnitude of difference in the standardized means between treatment and control. The tradeoff for more precise balance is a larger variance in the weights. In our base analysis, we will use weights that tolerate a difference in the standardized means in age, sex, and race up to 0.001 standard deviations between treatment and control. In sensitivity analyses, we will loosen the tolerance in constructing these weights to 0.01 standard deviations between treatment and control. The balance weights are calibrated to match the characteristics of the overall study population. This method has been shown to perform better than a model-based approach that fits a propensity score.⁹ Once we deploy the sample balance weights, all demographic characteristics are balanced. Job characteristics, including prevalence of Cigna insurance, are balanced in all analytical subsamples.

Table 9 examines individual-level characteristics collapsed to the worksite level, as well as county-level characteristics, using 2015 data from the U.S. Census Bureau. This suggests that the employee pools at the worksites roughly reflect the characteristics of the local population. The fact that treatment and control groups were located in idiosyncratically different parts of the country can be appreciated from **Figure 1**, where, for example, worksites in Ohio and Virginia were disproportionately randomly assigned to treatment and worksites in Florida were more likely to be randomly assigned to control.

VI. Statistical Analyses

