In this representative estimating equation, Y_{ijt} denotes an outcome of interest, such as medical spending, for individual i who is employed in worksite j at time t . $TREATMENT_{jt}$ is a binary indicator of whether the individual's worksite was randomized into treatment or control. We assigned each individual to the worksite at which he or she was employed when the treatment began in January 2015. $TIME_WORKED_{ijt}$ is the share of total available work hours in the study period that the individual actually worked; it is expressed in percentage terms. The effect of randomization to a treatment worksite is allowed to vary based on exposure to the treatment (measured via time worked during the treatment period). The treatment effect is captured by $\beta_1 + \beta_3 * Exposure$. The average effect of randomization into the treatment group can be summarized by assessing this at the average level of exposure. While we will produce estimates of the average effect of randomization into treatment, as captured in the layout of Tables 3-6, we will additionally show results for both β_1 and β_3 for each of our results in a set of parallel tables.

X_{ijt} represents a vector of covariates that may help improve precision as well as account for chance differences in characteristics between treatment and control groups, including:

- Age indicators: <20 years (omitted), 20-29, 30-39, 40-49, 50-59, and 60 and greater.
- Sex indicator: male (omitted), female
- Age-sex interactions
- Race: white (omitted), black, Hispanic, and other
- Employment characteristics (measured at baseline for the stably employed subsample):
 - Part-time (omitted), full-time
 - Salaried (omitted), hourly
 - Sales worker (omitted), non-sales worker, and other worker.

ε_{ijt} is the idiosyncratic error term. The models are weighted using the sample weights described above. Standard errors were clustered at the worksite level.

B. Local average treatment effect (LATE)

While our ITT analysis explores the effect of being randomized into a treatment worksite, a related but distinct question is: what is the effect of participating in the wellness program on the outcomes of interest? The answer to this second question will be different if not all employees in treatment worksites elect to participate. Because the choice to participate in the program is endogenous, simply including participation as a right-hand side variable may produce biased

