estimates of the effect of the treatment. Therefore, we model the impact of participation on outcomes using a two-stage least squares (2SLS) specification:

$$Y_{ijt} = \gamma_0 + \gamma_1 PARTICIPATION_{ijt} + \gamma_2 X_{ijt} + \mu_{ijt} \quad (3)$$

Where the endogenous *PARTICIPATION* variable is estimated via the first stage regression:

$$PARTICIPATION_{ijt} = \pi_0 + \pi_1 TREATMENT_{jt} + \pi_2 TIME_WORKED_{ijt} + \pi_3 TREATMENT_{jt} * TIME_WORKED_{ijt} + \pi_4 X_{ijt} + v_{ijt} \quad (4)$$

We include the exposure interaction in the first stage, parallel to our ITT estimates. The coefficient γ_1 in equation (3) identifies the effect of participation on outcomes.

On the left-hand side of the first stage, this base specification uses the continuous definition of participation, with values from 0-12, which indicates the number of modules an individual participated in during the 36-month study period. **Table 10** shows the results of first stage estimates for this and for our alternative definitions of participation (including indicators for completion of 3 or more modules of the program or completion of at least 1 module of the program). In robustness specifications, we use these alternative definitions of participation.

If no one in the control group receives the treatment, we can interpret the 2SLS estimates of the LATE as a treatment on the treated (TOT). Empirically, we expected this to be essentially true by construction because the control worksites did not receive the wellness modules. However, because we assigned employees to worksites based on their initial locations of employment at the beginning of the study period, a small number of employees who moved from control worksites to treatment worksites during the intervention period did receive an opportunity to participate in the program. This explains the fact that the control group means in **Table 10** are nearly, but not exactly, zero.

C. Addressing endogeneity concerns

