Notes: Table reports the coefficient on TREATMENT from estimating equation (1) by OLS (column 2), and the coefficient on PARTICIPATION from estimating equation (2) by IV (column 3). Standard errors are listed in parentheses. Column 1 reports the mean of each outcome in the control group for each sample (with standard deviation in parentheses). All regressions include demographic and employment controls (age, sex, age-sex interactions, race/ethnicity, full-time status, paid hourly status, and job category) and cluster standard errors at the worksite (for employee-level regressions). Employee-level and stably employed subsample control means are weighted by a weight that balances treatment and control on demographic characteristics. Worksite-level control means are not traditionally weighted: individual-level records are collapsed at the worksite-level and weighted by the total number of hours worked at each worksite.

Table 5: Impact on Biometrics

	Employee-level			Stably Employed Subsample		
	Mean in Control Group (1)	Reduced Form (Linear) (2)	2SLS (Linear) (3)	Mean in Control Group (1)	Reduced Form (Linear) (2)	2SLS (Linear) (3)
Cholesterol (mg/dl)	179.87 (38.71) 1,392			184.88 (37.85) 739		
HDL (mg/dl)	49.47 (14.58) 1,366			50.51 (14.87) 720		
Glucose (mg/dl)	104.76 (35.71) 1390			105.79 (38.17) 736		
Systolic BP (mmHg)	124.84 (18.55) 1,400			127.22 (18.73) 738		
BMI	29.79 (7.27) 1,403			30.04 (6.71) 742		

Notes: Table reports the coefficient on TREATMENT from estimating equation (1) by OLS (column 2), and the coefficient on PARTICIPATION from estimating equation (2) by IV (column 3). Standard errors are listed in parentheses. Column 1 reports the mean of each biometric outcome in the control group for each sample (with standard deviation in parentheses, followed by the number of observations for each outcome). All regressions include demographic and employment controls (age, sex, age-sex interactions, race/ethnicity, Cigna coverage status, full-time status, paid hourly status, and job category) and cluster standard errors at the worksite (for employee-level regressions). Control means are weighted by a weight that balances treatment and control on demographic characteristics.

Table 6: Impact on Self-Reported PHA Responses

	Employee-level			Stably Employed Subsample		
	Mean in Control Group (1)	Reduced Form (Linear) (2)	2SLS (Linear) (3)	Mean in Control Group (1)	Reduced Form (Linear) (2)	2SLS (Linear) (3)
Domain 1: Health Behaviors						

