	Treatment (n=2344)	Primary Control (n=2378)	Primary + Secondary Control (n=13000)	(1) vs (2) P value	(1) vs (3) P value
Demographics					
Age (yrs)	39.0	38.1	38.7	0.193	0.623
Female (%)	47.4	47.7	46.9	0.905	0.747
Race (%)				0.998	>0.999
Black	20.5	18.1	20.3		
White	57.9	60.5	56.2		
Hispanic	16.2	17.4	17.7		
Other	5.4	4.0	5.8		
Employment					
Worker type (%)				>0.999	>0.999
FT salary	11.7	11.8	12.0		
FT hourly	36.2	37.3	38.2		
PT hourly	52.1	50.9	49.9		
Annual rate (\$)					
FT salary	49,304	47,910	48,301	0.178	0.218
FT hourly	24,933	24,237	24,773	0.285	0.764
PT hourly	10,142	9,944	10,027	0.220	0.430
Standard Hours Per Week				>0.999	>0.999
FT salary	40	40	40		
FT hourly	35.6	35.6	35.8		
PT hourly	20	20	20		
Job Category				>0.999	>0.999
Sales workers	38.1	38.3	37.8		
Laborers/Helpers	18.9	17.8	18.4		
Operatives	15.7	15.1	15.4		
Service workers	12.3	13.1	12.5		
First/Mid level officials	9.2	9.2	9.4		
Admin Support	3.8	3.9	4.2		
Other	2.1	2.6	2.2		
Health Insurance					
Ever Enrolled in Cigna (2014)	0.4	0.4	0.4	0.964	0.244
Months in Cigna	11.4	11.3	11.4	0.834	0.607
Total medical spending	5,476	3,634	4,659	0.135	0.493

Notes: Employees are included if they were part of the stably employed subsample. Health insurance variables are pre-randomization characteristics. Demographics and employment characteristics are taken from the Team Member database supplied by BJ's and based on the first entry for an individual during the treatment period. Age is defined as of December, 2014 (pre-treatment) and employees who were under 18 are excluded. Column 1 reports the means for employees in the treatment group while columns 2 and 3 report the means for the

primary control employees and all control employees (primary and secondary), respectively. Treatment status is defined by the first worksite an employee appears in during the treatment period. Column 4 reports the p-value for the comparison between the employees at treatment worksites and the employees at primary control worksites and column 5 reports the p-value for the comparison between the employees at treatment worksites and all employees at control worksites. All regressions are weighted by a weight that balances treatment and control on demographic characteristics and cluster standard errors by worksite.

Table 9: Balance Between Treatment and Control—Worksite Level

	(1)	(2)	(3)		
	Treatment	Primary Control	Primary + Secondary Control	(1) vs (2)	(1) vs (3)
	(n=25)	(n=25)	(n=135)	P value	P value

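### The stably employed Cigna medical spending models leave out pre-randomisation medical spending, which the trial already holds; adding it would not correct a bias but could narrow the interval

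*Combined protocol and SAP*

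**What the plan says.** Section VI.A gives the covariate vector X two purposes: it "represents a vector of covariates that may help improve precision as well as account for chance differences in characteristics between treatment and control groups". The list that follows holds age, sex, age-sex interactions, race and employment characteristics. It is introduced as a list of examples, but the Table 4 notes close it for the spending outcomes: "All regressions include demographic and employment controls (age, sex, age-sex interactions, race/ethnicity, full-time status, paid hourly status, and job category", with nothing after job category.

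The same X enters both 2SLS stages (equations 3 and 4). On the first stage the plan adds only this: "We include the exposure interaction in the first stage, parallel to our ITT estimates". The weights in Section V.B were "constructed to balance treatment and control samples on age, sex, and race while minimizing variance of the weights". Section VI.F varies the functional form, the definition of participation and the phase 1 specification, but adds no model with prior spending.

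The variable exists. The health insurance block of Table 8 Panel D (stably employed, demographic weights applied) reports total medical spending of $5,476 in treatment, $3,634 in primary controls (p = 0.135) and $4,659 in all controls (p = 0.493). The note states: "Health insurance variables are pre-randomization characteristics". The plan uses the figure only to describe balance.

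**The concern.** Medical spending is a very noisy outcome. Among stably employed Cigna controls the SD is $19,057 on a mean of $4,722 (Table 4). Age, sex, race and job type are indirect predictors. A person's own earlier spending is the direct one and can be expected to predict later spending, whatever the observed gap between arms. Section VI.C says that imbalance in covariates that affect outcomes is a threat, and that observed covariates are controlled for; this one is observed and is not controlled.

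The stake is interval width. Phase 1 found no significant effect on spending, so the value of a second null result depends on which effects the interval can exclude. Showing the baseline gap in a balance table does nothing for precision.

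The point is confined to the stably employed Cigna subsample. The plan says "Our main study sample comprised all employees who worked for any duration of time", so the main sample includes later hires who can have no baseline value.

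**Working it through.** The documents state no power, detectable effect or baseline-outcome correlation for spending, so there is no design figure to reproduce. The p-value of 0.493 cannot be rebuilt either, because Panel D gives no SD.

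**1. The Panel D gap.** All controls are the comparator, because Section III includes the secondary control sites in analyses of administrative data.
- Gap = 5,476 − 4,659 = $817 (17.5% of 4,659).
- p = 0.493 gives z = 0.6855, so the implied clustered SE = 817 / 0.6855 = $1,192.
- 95% interval = 817 ± 1.96 × 1,192 = −$1,519 to +$3,153.

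This is compatible with chance.

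**2. Whom the baseline mean describes.** Panel D does not say. In the row "Months in Cigna" the all-control mean is 11.4. Averaged over all stably employed staff, of whom 0.4 were enrolled in 2014, it could be at most 0.4 × 12 = 4.8 (5.4 if 0.4 is rounded down from 0.45). Likewise, $4,659 averaged over all staff would imply 4,659 / 0.4 = $11,648 per enrollee, about 2.5 times the Table 4 control mean of $4,721.85; $4,659 itself lies within 1.3% of that mean. This supports, without proving, a mean per 2014 enrollee.

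**3. Coverage.** The analysis has 6,907 people (Table 10 Panel B): 5,779 control and 1,128 treatment. Expected 2014 enrollees among the 15,344 stably employed: 0.4 × 15,344 = 6,138. If all were among those analysed, coverage would be 6,138 / 6,907 = 89% (78% to 100% for 0.35 to 0.45). The actual overlap is not given, so 50% is added as an illustration.

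**4. Precision gain.** With coverage c and correlation r among those covered (taken after the other covariates), the fall in SE is 1 − √(1 − c·r²). This assumes the same residual variance in staff without a baseline value and the same proportional gain at worksite level. The range for r is an assumption.

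| Coverage c | r = 0.2 | r = 0.6 |
|---|---|---|
| 100% | 2.0% | 20.0% |
| 89% | 1.8% | 17.6% |
| 50% | 1.0% | 9.4% |

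**5. What that means for the outcome.** Ignoring clustering and weights, SE = 19,056.92 × √(1/5,779 + 1/1,128) = $620. The effect detectable with 80% power at two-sided 5% is 2.80 × 620 = about $1,738, or 36.8% of the control mean. At full coverage it falls to $1,703 for r = 0.2 and $1,390 (29.4%) for r = 0.6. Clustering and weighting would probably make the absolute figures larger.

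**The case against.** The strongest reply is that nothing here is an error. The planned model is valid without prior spending, and the observed gap looks like chance. The gain rests on a correlation the documents do not give, and at the low end a 1 to 2% change in SE would alter no conclusion. All of that stands. It limits the point to an improvement in efficiency, but does not answer it, since chance differences and precision are the plan's own reasons for having X. A balance p-value also does not show whether a covariate predicts the outcome.

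A second reply also stands. Treatment was assigned by worksite. If between-worksite variation drives the SE, the saving depends on the worksite-level association between prior and later spending, which is unknown.

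A reader might go further and multiply the $817 by an assumed slope of 0.2 to 0.6, concluding that $163 to $490 stays in the estimate and masks a saving. The documents do not support that, for three reasons:
- **The slope is unknown.** Using one range for slope and correlation assumes equal baseline and outcome SDs. With the Table 4 SD as a stand-in and 35 to 45% enrolled, the naive SE of the gap is $637 to $723, so the implied $1,192 is 1.65 to 1.87 times as large. If a larger baseline SD explains this, slopes become 0.2/1.87 to 0.6/1.65, or 0.11 to 0.36, and the product becomes about $87 to $297. If clustering or weights explain it, that correction does not apply. The documents cannot separate these.
- **The gap is not conditional on X.** Panel D is weighted on demographics only, as far as its notes say. The model also adjusts for full-time status, pay type, job category and time worked. Control spending differs by employment type ($5,163 full-time, $2,993 part-time, Table 11), and Panel D shows 52.1% part-time in treatment against 49.9% in all controls.
- **The people differ.** Panel D appears to describe 2014 enrollees, not the 6,907 analysed.

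**Conclusion.** The omission is real and the plan's own stated purpose for X argues against it. It is a missed gain in precision, not a flaw that invalidates the analysis. Over repeated randomisation the intention-to-treat estimator is unbiased with or without the baseline term.

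For an assumed correlation of 0.2 to 0.6, the SE would fall by about 2 to 20% at full coverage and 1 to 9% at 50% coverage, if the association also holds at worksite level. The low end is negligible and the high end worthwhile; the documents cannot say which applies, but the control-group data can.

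Two stronger readings should be resisted. A reader might infer from $5,476 against $4,659, or from the wider primary-control gap of $1,842, that randomisation failed or that the spending estimate is biased; p-values of 0.493 and 0.135 do not show that, and primary controls alone are not the comparator for claims outcomes. Nor can a firm dollar carry-over be stated, since both the baseline SD and the gap among those analysed, given the other model terms, are unknown.

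**What to change.** Before outcomes are compared by arm, amend the stably employed Cigna medical spending models as follows:
- Add 2014 total medical spending, annualised by the rule used for the outcome, plus an indicator for staff with no baseline value, to equation (1) and to both 2SLS stages (equations 3 and 4).
- Fix one functional form in advance (raw, log(1+x), or capped at a stated percentile), chosen from control-group data only. Section I says the authors have already examined control-group outcomes.
- Report how many of the 6,907 have a baseline value, and the control-group slope of later on prior spending.
- Keep the current X as a sensitivity analysis.

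The cost is SAP wording and two model terms, with no new data collection. The form, any cap and the missing-value rule are further choices to fix in advance, which matters in a plan written to limit specification searching. If the control-group correlation proves low, the gain will be small.
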